### 8.3.2. Study discontinuation

For patients prematurely discontinuing the study, date and reason of withdrawal must be recorded in the eCRF. Only non-evaluable patients will be replaced, as appropriate.

#### 8.3.2.1. End of treatment

Treatment with Debio 1143 will be continued until any of the following occurs:

1. Unacceptable toxicity [including, treatment-related NCI-CTCAE v5.0 grade 4 laboratory abnormalities (excluding hematological and/or non-febrile asymptomatic neutropenia/leukopenia)] that does not resolve with appropriate standard medical measures; or intercurrent illness that would, in the opinion of the Investigator, affect assessments of clinical status to a significant degree or compromise the patient's safety;
2. Permanent discontinuation of nivolumab;
3. Treatment delay greater than 4 and 8 weeks (+1-week tolerance) for Debio 1143 and nivolumab, respectively;
4. Need to discontinue Debio 1143 due to toxicity despite dose reduction to 100 mg/d;
5. Prohibited medication as indicated in [section 7.7.2](#) is required/used during the course of the trial. In the event a patient is found to be taking a prohibited medication during the trial, the site should immediately contact the medical monitor. The decision to withdraw the patient will be made in conjunction with the Sponsor;
6. If a critical protocol violation occurs that may preclude safety continuation of the study for the patient, the Sponsor's trial manager will be contacted to discuss if the patient has to be withdrawn from treatment;
7. Symptomatic disease progression documented by RECIST v1.1 or by GCIG criteria (Cohort 4, if applicable) in RECIST non-evaluable patients. However, patients may continue study treatment if, in the Investigator's opinion, there is reasonable evidence of ongoing clinical benefit or suggestion of "pseudoprogression" without excess risk of toxicity or complications for the patients.
8. Confirmed disease progression as per iRECIST;
9. Any medical condition that the Investigator or Sponsor determines may jeopardize the patient's safety if he or she continues in the study;
10. Withdrawal of patient's consent;
11. Pregnancy or breast-feeding a baby;
12. Start of any subsequent anti-neoplastic therapy (excluding palliative symptomatic localized RT up to 36 Gy total doses for alleviating symptoms e.g. pain, intracranial hypertension, which may continue upon the Sponsor's agreement, if appropriate). These patients will continue only in the OS follow-up.

Patients who discontinue treatment for any of the reasons above will have an EOT visit performed 30 days ( $\pm$  5 days) after the last Debio 1143 administration date, but prior to any further therapeutic intervention, whenever possible, otherwise an EOT visit should be ideally scheduled immediately before these events. Results of these assessments are to be recorded in the eCRF, together with the reason for treatment discontinuation.

[figure not shown]
Patients who are taken off study treatment due to AEs are to be treated and followed up according to accepted medical practice. All pertinent information concerning the outcome of such treatment is to be recorded in the eCRF.

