# From Cycle 3, a switch to 480 mg q4w (Day 1 of each 28-day cycle) will be allowed on a per-patient basis, based on the Investigator's judgement and Sponsor's agreement. Once the nivolumab dose is switched, this schedule should be maintained until EOT.

In Part B, patients will receive Debio 1143 at the RP2D established in Part A, in combination with nivolumab at the standard dose. Per-patient dose adjustments of Debio 1143 will be considered according to the severity of any eventual observed toxicity (See [Section 5.4](#))

Participants are planned to be treated with Debio 1143 and nivolumab for up to 52 weeks (i.e., 13 cycles), until any of the following events occurs: symptomatic progressive disease (PD), asymptomatic but confirmed PD (as per iRECIST), unacceptable toxicity (per Investigator judgment and despite up to two dose adjustments), patient withdrawal, or treatment delay greater than 4 and 8 weeks (+1 week tolerance) for Debio 1143 and nivolumab, respectively (see [section 8.3.2.1](#) for details).

Permission to prolong the study treatment for one additional year can be exceptionally granted by the Sponsor, if patients are deriving continuous clinical benefit from the study treatment. Medical justification for extending the treatment and the assessment of the risk/benefit balance must be provided by the Study Investigator and will be discussed with the Sponsor. The decision to further extend study treatment will be re-evaluated on a yearly basis for each patient.

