#### 5.4. Dose modifications

For participants without DLT in the previous cycle and/or unacceptable toxicity, in the absence of symptomatic disease progression or confirmed iRECIST PD, the combination therapy can be continued unchanged as long as re-treatment criteria are met (cf. [Table 5-3](#)).

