## 8.2. Study assessments

### 8.2.1. Efficacy

Tumors will be assessed according to either RECIST version 1.1 guidelines by CT scan or MRI imaging of the target/non target lesions (38), and/or GCIG criteria using the serum marker CA-125 for Cohort 4, if applicable.(39)

CT scan and MRI will be performed at screening, then every 8 weeks ( $\pm$  1-week tolerance window) during the first 10 cycles, then every 12 weeks ( $\pm$  1 week) from Cycle 13 until symptomatic PD or confirmed iRECIST PD or start of any new cancer treatment or end-of-life care or end of the Main study period, whichever occurs first. For patients who exceptionally continue study treatment after completion of 13 cycles, tumor response assessments will continue at 12-week intervals ( $\pm$  1 week window) until the end of the Main study period, and thereafter at the frequency of local institutional care practice until PD, start of any new anticancer therapy, death or EOT.

Imaging will be performed as per site standard but whenever possible using contrast agent at screening and during treatment

CA-125 dosages will be performed at screening exclusively in patients included in Cohort 4. In case of abnormally elevated levels before treatment start, these dosages will be repeated on Day 1 of each subsequent cycle.

In case of response, efficacy assessments will be repeated 4 weeks later after first documentation (+ 1-week tolerance window). All patients will have an efficacy assessment (CT scan/MRI or serum CA-125 dosage) at the time of disease progression and/or treatment discontinuation, whichever occurs first.

As an exploratory analysis, tumor response will also be assessed using the iRECIST criteria (novel modified RECIST v1.1 guideline for immunotherapeutics).(40) These exploratory analyses will be described in the SAP.

Patients with asymptomatic, but radiologically observed unconfirmed PD as per iRECIST, may continue the study treatment, upon both the Investigator's request and the Sponsor's agreement, until PD is confirmed as per iRECIST or symptoms occurs or Investigator/patient decision to withdraw treatment, whichever occurs first.

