- 4 Every 8 weeks (±1 week) from first on-treatment scan until Cycle 10, then from Cycle 13, every 12 weeks (± 1 week) until confirmed iRECIST PD, symptomatic PD or any new anticancer treatment or end-of-life hospice care is started or until the end of the Main study period whichever occurs first. For patients who continue study treatment in the Extended study period, tumor response assessments will be performed at the frequency of local institutional care practice until EOT. All patients will have CT or MRI at the time of disease progression, if none previously available. CT or MRI done before screening, as part of patient's standard of care and not older than 8 weeks (+1-week tolerance) before C1D1 can be used instead of repeating a new assessment at screening even if done before ICF signature with patient specific agreement, if deemed clinically appropriate by the Investigator. A contrast enhanced brain CT or MRI is mandatorily at baseline only in SCLC cohort, subsequent brain scans to be done if clinically indicated.
- 5 Up to 3 tumor tissue samples will be collected:
- 1) An archived biopsy at diagnosis (before prior PD-1/PD-L1 therapy) = optional;
- 2) An archived biopsy if collected after prior PD1/PD-L1 or, if not available a fresh biopsy collected at screening will be mandatory;
- 3) A fresh biopsy collected at end of Cycle 2 (day 28=Day 1 of the following cycle) = optional
- 6 Timepoints as specified in Table 8-1, Table 8-2 and Table 8-3 and windows of tolerance as specified in Table 8-5.
- 6a Patients included in Part A only.
- 6b Debio 1143 PK, nivolumab PK, and nivolumab ADA sample at C6D1 only. In addition, for patients discontinuing the study at the end of the Main study period, the last nivolumab ADA will be collected at EOT, and for patients entering the Extended study period, the last nivolumab ADA will be collected at C13D1 instead of at EOT.
- 7 Timepoints as specified in Table 8-4 and windows of tolerance as specified in Table 8-5.
- 7a Only at Cycle 6: PGx ctDNA.

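### Section 8.3.2.1 lets patients stay on treatment after symptomatic progression, against the synopsis and section 8.2.1, and no repeat on-treatment scan is scheduled for them in the Main study period

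*Protocol*

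**What the plan says.** **Treatment at progression**

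- Protocol synopsis, Treatment Duration: symptomatic progression ends treatment. No exception is given and no other section is cited.
- Protocol 5.3: treatment runs "until any of the following events occurs: symptomatic progressive disease (PD), asymptomatic but confirmed PD (as per iRECIST", among other events. The sentence refers to section 8.3.2.1 for details.
- Protocol 5.4: therapy may go on unchanged "in the absence of symptomatic disease progression or confirmed iRECIST PD", provided the re-treatment criteria are met.
- Protocol 8.2.1: "Patients with asymptomatic, but radiologically observed unconfirmed PD as per iRECIST, may continue the study treatment". Both the investigator's request and the sponsor's agreement are needed, and this permission lapses once progression is confirmed or symptoms appear.
- Protocol 8.3.2.1, item 7, lists as an end-of-treatment event: "Symptomatic disease progression documented by RECIST v1.1 or by GCIG criteria (Cohort 4, if applicable) in RECIST non-evaluable patients". It then allows treatment to go on where the investigator believes that "there is reasonable evidence of ongoing clinical benefit or suggestion of" pseudoprogression, provided there is no excess risk. Only the investigator is named as deciding.
- Protocol 8.3.2.1, item 8: confirmed iRECIST progression also ends treatment.

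**Imaging**

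- Protocol 8.2.1 and footnote 4 of Tables 1-1 and 8-6: scheduled CT/MRI continues "until confirmed iRECIST PD, symptomatic PD or any new anticancer treatment" (footnote wording; 8.2.1 is to the same effect). The # footnote of both tables has the same stop for follow-up scans.
- Protocol 11.4.1.1: efficacy assessments stop at progression, without the symptomatic qualifier.
- Protocol 8.3.2.2: patients without progression at the end-of-treatment visit stay on 12-weekly imaging.

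**The concern.** The approval requirements run the wrong way round for a coherent rule. A patient without symptoms needs the sponsor's agreement to be treated past an unconfirmed progression; a patient with symptoms and documented progression needs only the investigator's opinion. A patient who loses the 8.2.1 permission because symptoms have appeared can be kept on treatment under item 7. Two sites could handle the same patient differently and each point to the protocol.

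The imaging rules do not recognise item 7. One of its two grounds for continuing is suspected pseudoprogression, which only a later scan can bear out or refute. Item 8 also depends on a later scan. The SAP assumes that such data exist: section 17.3.1.1 follows patients by iRECIST after a first RECIST progression, and the alternative spider plot in 17.3.2 runs to confirmed iRECIST progression, death or loss to follow-up. If the scans are not scheduled, the stop rule cannot work as intended, and the exploratory iRECIST result depends on which patients happened to be scanned.

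**Working it through.** There is no figure in the plan to reproduce. The check is a comparison of the rules.

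**Step 1: may a patient with documented symptomatic progression stay on treatment?**

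| Place | Answer | Approval named |
|---|---|---|
| Synopsis, Treatment Duration | No | None |
| 5.3 | No, but refers to 8.3.2.1 | None |
| 5.4 | Not among those who may continue unchanged | None |
| 8.2.1 | Not covered; the asymptomatic permission ends at symptoms | Investigator and sponsor (asymptomatic case) |
| 8.3.2.1 item 7 | Yes, for benefit or suspected pseudoprogression | Investigator only |

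The synopsis and item 7 give opposite answers. Section 8.2.1 and item 7 differ both on what the onset of symptoms does and on who must agree.

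**Step 2: is a later scan scheduled for that patient?**

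- The regular 8-weekly and 12-weekly scans stop at symptomatic progression (8.2.1, footnote 4) or at any progression (11.4.1.1).
- A scan is required at progression if none is available (footnote 4). That is the scan that documents the event, not a repeat.
- Section 8.2.1 asks for an assessment at the earlier of progression and discontinuation. Progression satisfies it for a patient who then continues.
- Tables 1-1 and 8-6 mark CT/MRI at the end-of-treatment visit, but footnote 4 governs the whole row.
- In the Extended study period, footnote 4 keeps assessments going at local frequency until end of treatment.
- For patients treated beyond 13 cycles, one sentence of 8.2.1 keeps 12-weekly assessments to the end of the Main study period without repeating the progression stop. It might be read as restoring scans for someone who got that far, against footnote 4. It gives nothing before then.

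So no repeat on-treatment scan is clearly scheduled in the Main study period for a patient continued under item 7.

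**Step 3: how long could this last?** As a ceiling only, assume that symptomatic progression is documented at week 8. Planned treatment is 13 cycles × 4 weeks = 52 weeks, which leaves 52 − 8 = 44 weeks. The 8-weekly schedule would otherwise have placed scans at weeks 16, 24, 32 and 40, followed by the Cycle 13 scan. Most patients would be stopped well before that by other rules.

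**Step 4: which results depend on it?** Protocol 11.4.1.1 counts objective response only until progression, and SAP 17.2.1.5 dates PFS at the first documented progression. Later scans therefore add little to either. Exposure, adverse events while on drug, item 8 and iRECIST best response (SAP 17.3.1.1) do depend on what happens afterwards.

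**The case against.** The best defence is that section 5.3 refers to 8.3.2.1 for details, so item 7 is the detailed rule with its exception and there is no conflict between those two sections. That stands as far as it goes. Section 5.4, likewise, only sets conditions for continuing unchanged and does not itself end treatment. Neither point helps with the synopsis, which has no such reference, or with 8.2.1, which ends its permission at symptoms and requires the sponsor's agreement.

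On imaging, SAP 7.4 brings unscheduled tumour assessments into the section 17 analyses, so a scan done on clinical grounds would be used. That softens the loss, but leaves it to each site whether the scan happens.

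Stronger readings are tempting, and the documents do not support them:

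- *That these patients have no tumour assessment at all.* A scan at progression is required if none is available, and the Extended study period has its own provision.
- *That every patient with symptomatic progression is affected.* Item 7 reaches only those with apparent benefit or suspected pseudoprogression and no excess risk. ECOG-PS of at most 1 on Days 1 and 15 (Table 5-3) and the safety stop in item 9 narrow it further.
- *That this is the commonest reason for stopping treatment.* The documents give no such frequency.
- *That the primary result is compromised.* Response and PFS are counted to first progression.

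**Conclusion.** The inconsistency is real and should be corrected. It lies mainly between the synopsis and section 8.2.1 on one side and item 7 of section 8.3.2.1 on the other, together with a schedule that provides no repeat on-treatment scan in the Main study period for patients whom item 7 keeps on treatment.

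Its size cannot be put as a number. Part B plans 32 to 60 evaluable patients and Part A 3 to 12, but nothing in the documents says how many would progress with symptoms and then be continued. The consequences are uneven handling of patients between sites, exposure and safety data that depend on which section was followed, a stop rule (item 8) without its scheduled input, and a less evaluable exploratory iRECIST best response.

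The statement that the primary analysis is largely unaffected rests on the protocol's cut-off at progression in 11.4.1.1. SAP 17.2.1.2 and 17.2.1.3 do not restate that cut-off and name new therapy as the limit. However, 17.2.1.3 derives confirmed response by RECIST 1.1, and the comparison table in protocol Appendix C does not allow a RECIST 1.1 response after progression.

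**What to change.** Reconcile the synopsis and sections 5.3, 5.4, 8.2.1 and 8.3.2.1 so that one rule and one approval path apply at symptomatic progression. Which rule that is remains the sponsor's clinical decision.

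Then bring the imaging-stop wording in 8.2.1, 11.4.1.1 and the footnotes to Tables 1-1 and 8-6 into line with it, so that scheduled tumour assessments cover any period in which the retained rule allows treatment after progression. The end of imaging should not simply be tied to the end of treatment: read literally, that would remove the 12-weekly scans that 8.3.2.2 requires after end of treatment for patients without progression, and PFS needs those.

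The cost is protocol wording and, if treatment after symptomatic progression is kept, possibly a few routine scans.

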### 8.3.2.2. Follow-up

Patients with confirmed PD at the EOT visit will have an safety follow-up of 5 months ( $\pm 15$  days) planned after the last nivolumab infusion, provided no new cancer treatment or end-of-life care has been started, otherwise this visit may be done immediately before if any of these occur. Patients without PD documented at the EOT visit will continue in follow-up for efficacy every 12 weeks ( $\pm 1$ -week window) until PD or start of new treatment or end-of-life care, whichever occurs first. After PD or new cancer treatment or end-of-life care starts, patients will not attend more onsite visits, however, they and/or relatives may be contacted (by telephone, email or mail) every 4 ( $\pm 1$ ) months to update the survival status until the end of the Main study period (18 months have elapsed since the LPI was included in the study or 60 days after LPLV, whichever occurs first).

- Follow-up assessments comprise onsite visits:
- Safety: For all patients, one first safety follow-up visit will be conducted 90 days ( $\pm 15$  days) after last study treatment; a second safety follow-up visit will be scheduled at 5 months ( $\pm 15$  days) after the last nivolumab infusion, provided the first safety follow-up visit did not overlap ( $\pm 1$  week), and if the patient is still alive and no further anticancer treatment has been started yet..
- Efficacy: Patients without evidence of PD at EOT will be assessed for PD by appropriate methods (CT scan or MRI, and clinically) every 12 weeks ( $\pm 1$  week) until symptomatic PD or confirmed iRECIST PD or start of any new cancer treatment or end-of-life care or the end of the Main study period, whichever occurs first. For patients who continue study treatment after the Main study period, tumor response assessments will continue at the frequency of local institutional care practice until PD, start of any new anti-cancer therapy, death or EOT, whichever occurs first.
- Survival calls/contact: All patients alive after symptomatic progression or confirmed iRECIST PD or start of new anti-cancer treatment will be contacted (by telephone, e-mail or mail) every 4 ( $\pm 1$ ) months until the end of the Main study period. In case patients cannot be reached, the primary physician or the patient's partner or family may be contacted by the Investigator or designee.

The following scheme summarizes the temporal relationship between EOT and EOS:

EOS will occur at the End of Main study period or End of Extended study period, whichever occurs last. After the End of Main study period no OS follow-up will be performed for patients in the Extended study period.

#### **8.4. Study duration and EOS**

The study duration for an individual patient completing 13 cycles, will be 52 weeks plus up to 5 months for safety follow-up after EOT, excluding a 4-week screening period. Patients will attend the EOT as well as any follow-up visits, if applicable.

Permission to prolong the study treatment for one additional year can be exceptionally granted by the Sponsor, if patients are deriving continuous clinical benefit from the study treatment. Medical justification for extending the treatment and the assessment of the risk/benefit balance must be provided by the Study Investigator and will be discussed with the Sponsor. The decision to further extend study treatment will be re-evaluated on a yearly basis for each patient.

The total number of onsite visits per patient will depend on the total number of cycles delivered which is based on disease progression, clinical deterioration, investigator criteria, unacceptable toxicity or death whichever occurs first.

The EOS will occur at the End of Main study period or End of Extended study period, whichever occurs last.

The Sponsor will make every effort to supply Debio 1143 and nivolumab to patients who benefit from continued treatment; Safety of the patients will be monitored and Health authorities will be notified per regulatory requirements.

Patients will discontinue the study for any of the following reasons:

1. Patient withdrawal of consent;
2. Patient lost to follow-up;
3. Start of end-of-life care;
4. Death;
5. Sponsor or Institutional Review Board (IRB)/ Independent Ethics Committee(s) (IEC) decides to terminate early the study;
6. Completion of Main study period, or completion of Extended study period, as applicable.

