	
After PD or start of any new cancer treatment, follow-up for overall survival (OS) will be collected, by telephone, email or mail every 4 months (<math>\pm</math> 1 month) until the end of the Main study period.
 
There will be up to two visits planned for screening and at least two treatment visits per cycle on D1 and 15 up to Cycle 3, then at least one treatment visit from Cycle 4 onwards if applicable, plus one EOT <math>\pm</math> follow-up visit, as applicable. The total number of onsite visits per patient will depend on the total number of cycles delivered which is based on disease progression status, clinical deterioration, start of new cancer treatments or end-of-life care or death whichever occurs first.

STUDY VISITS & ASSESSMENTS	Cf. Figure 'Study plan' and Table 'schedule of assessments'
STUDY PERIOD	
First patient included (FPI): ~ Q1-2019  Dose optimization part: ~ 3 months  FPI Basket trial part: ~ Q2-2019  Assessment of the primary clinical endpoint for futility: ~ 6-9 months after FPI  Complete accrual in non-futile indications: ~ 3-9 months (according to results)  Accrual period: ~ from 9 to 18 months (depending on futility assessments)  End of the Main study period: 18 months after LPI or 60 days after last patient last visit (LPLV), whichever occurs first  Extended study period: Only for patients treated beyond 13 cycles. Starts after the Main study period and lasts until LPLV.  End of study (EOS): End of Main study period or End of Extended study period, whichever occurs last.  Final analysis (Final CSR): within 1 year of end of the Main study period. Data collected during the Extended study period will be summarized in an addendum to the Final CSR, after the End of Extended study period.

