**Follow-up:** A first follow-up (FU) visit is scheduled 90 (± 15) days after last study treatment, a second safety follow-up visit may be scheduled at 5 months (±15 days) after the last nivolumab infusion, provided the first safety follow-up visit did not overlap (± 1 week), and provided that no subsequent anticancer treatment or end-of-life hospice care had been started before. Subsequent visits will be scheduled every 12 weeks (± 1 week) after EOT unless confirmed or symptomatic PD occurred before or any new anticancer treatment or end-of-life care is started, whichever occurs first. Once PD occurs, or start of new treatment, phone calls, email or mail to document survival status will be done every 4 (± 1) months until the end of the Main study period (lasts until 18 months after LPI or 60 days after LPLV, whichever occurs first).

**EOS:** At the end of the Main study period or at LPLV if patients are ongoing in the Extended study period, whichever occurs last.

- \* Examinations should be performed in the following order as applicable: physical examination, vital signs, ECG, safety blood/urine samples, followed by blood sampling for PK/PDy according to specific instructions, and other examinations: Note: ECGs always have to be taken before PK/PDy sampling. Assessments should be performed on schedule, but occasional changes may be allowed. If the study schedule is shifted, both assessments and dosing must be shifted to ensure the collection of data is completed prior to dosing. **Windows:** Laboratory assessments and clinical examinations: Screening period: -4 days (i.e., day -32); EOT visit: ±5 days; follow up visits ±1 week, in case of holidays, vacations; other administrative reasons: ± 3 days in all cycles. Window for CT/MRI assessment = ± 1 week
- # Assessments for concomitant medications, pregnancy test and AEs will be performed only at the first two FU visits, if applicable. CT scan or MRI assessments will be performed until confirmed iRECIST PD, symptomatic PD or any new anticancer treatment or end-of-life hospice care is started or until EOS whichever occurs first.
- # Height only collected at screening.

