- 8 Debio 1143 will be taken orally on D1-10 and D15-24 on an empty stomach (patients will fast for 2 h before dosing and for at least 1 h after dosing) at approximately the same time each day. Water is permitted freely. A missed dose can be taken as soon as the patient remembers but no later than 6 h after the planned dose. If >6 h have elapsed, the missed dose should be skipped and the next dose taken according to the regular dosing schedule. A double dose should not be taken to make up for a missed dose. Debio1143 will be given in the hospital (before nivolumab infusion whenever is applicable) during: Cycle 1 on Days 1,3 (only Part A), 8, 15, 17 (only Part A), 22; Cycle 2 on Days 1 and 15; Cycle 3 on Days 1, 3 (only Part A), 15, and 17 (only Part A); and on Days 1 ± 15 of all subsequent cycles. The rest of the days will be taken at home following relevant medical instructions. A patient's diary to record treatment compliance will be provided as a separate document and it will be reconciled with the returning capsules by the study nurse.
- 9 Nivolumab will be administered, as per current prescribing information, at a dose of 240 mg, flat dose by IV infusion over at least 30 minutes on Days 1 and 15, every 4 weeks (i.e., 2 infusions in each cycle).
- 9a From Cycle 3 on, the switch to an administration of 480 mg of nivolumab only on Day 1 of each 28-day cycle is allowed based on the Investigator's judgment and Sponsor's agreement.
- ± Dispensing of nivolumab will depend on the nivolumab schedule administered from Cycle 3 onwards.

-  Continuous AE monitoring, with Investigator's assessment and documentation at scheduled study visits up to EOT visit and second follow up visit, if applicable. The SAE reporting period is up to 5 months after the last nivolumab administration. Patients continuing in follow-up (FU) after EOT, in the first and/or second FU visits will have final AEs update of any ongoing toxicity at this time, if applicable, unless start of new anticancer treatment or end-of-life-care, in which case visit should be scheduled ideally before.
-  For Part B, visits on Cycle 1 and Cycle 3 on Days 3 and 17 will not be performed
-  Including information on current and previous tobacco and alcohol use/consumption
-  Only applicable for patients treated beyond Cycle 13

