### 9.2.2. Reporting post-study

Any SAE occurring up to 5 months from the last nivolumab infusion date will be reported in the appropriate eCRF pages and within one day of SAE awareness as described in [section 9.2.1](#)

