## 9.3. Follow-up of serious adverse events

All SAEs, regardless of severity, must be followed up:

- To resolution (the patient's health has returned to the baseline status or all variables have returned to normal), or
- Until stabilization of the event has occurred (the Investigator does not expect any further improvement or worsening of the event), or
- Until the event is otherwise explained regardless of whether the patient is still participating in the study.

Some events, such as metastases, are often ongoing; however, once these events have been determined by the principal Investigator to be stable or chronic, he/she may consider the event to be resolved or resolved with sequelae.

The Investigator will notify the Sponsor of any follow-up information in the eCRF pages within 24 hours of new information awareness (see [section 9.2.1](#)).

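### Protocol 8.4 ends study participation when end-of-life care begins, against the survival follow-up in 8.3.2.2; read literally, it would bias the secondary OS estimates upward

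*Protocol*

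**What the plan says.** Protocol 8.4 (Study duration and EOS) introduces six reasons with "Patients will discontinue the study for any of the following reasons". Item 3 is the start of end-of-life care. It is separate from death (item 4) and sits beside consent withdrawal and loss to follow-up. Nothing is said about survival status.

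Protocol 8.3.2.2 (Follow-up) treats the same event differently. Once the patient progresses, starts a new treatment "or end-of-life care starts, patients will not attend more onsite visits, however, they and/or relatives may be contacted" every four months or so for survival status, until the Main study period ends. A later bullet in that section is mandatory for a defined group: "All patients alive after symptomatic progression or confirmed iRECIST PD or start of new anti-cancer treatment will be contacted".

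Two other places continue survival contact and do not stop it at end-of-life care. The synopsis (Participant duration) has "After PD or start of any new cancer treatment, follow-up for overall survival (OS) will be collected". The follow-up notes to Tables 1-1 and 8-6 have "Once PD occurs, or start of new treatment, phone calls, email or mail to document survival status will be done". Neither names end-of-life care as a trigger.

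In the SAP, 17.2.1.7 censors a patient without a documented death at the latest date on which the patient is known to have been alive. Section 17.2.4 has two OS sensitivity analyses, one for new systemic therapy and one for COVID-19 deaths. Neither concerns patients closed for end-of-life care.

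**The concern.** Items 1, 2 and 4 of the 8.4 list all end data collection, so a site could reasonably read item 3 the same way. Elsewhere the protocol says so when OS follow-up is meant to outlast an event: 8.3.2.1 item 12 keeps patients who start new therapy in OS follow-up, and 11.4.1.1 excepts OS when other efficacy data stop. Item 3 carries no such exception.

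End-of-life care predicts imminent death. Closing a patient there and censoring at the last contact takes out of the risk set someone whose hazard is far above that of the patients who remain. Kaplan-Meier assumes the opposite, so the curve would sit too high. In a single-arm trial no control group shares the error. At stake are median OS and the 12- and 18-month OS rates, all secondary and descriptive.

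**Working it through.** The documents give no expected OS, OS event count or OS precision target, so there is no planned figure to reproduce. The check is a reading of the passages, followed by algebra for the direction.

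**1. Who is affected**

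- Patients with symptomatic or iRECIST-confirmed progression, or new therapy, who later enter end-of-life care: the 8.3.2.2 bullet requires contact to the end of the Main study period. Item 3 contradicts a mandatory rule.
- Patients who enter end-of-life care with none of these: only the permissive sentence in 8.3.2.2 covers them. Item 3 contradicts a permission, and even without item 3 nobody is obliged to call.

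**2. Other routes to a death date if contact stops**

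- SAP 18.2 takes deaths from a dedicated eCRF Death page. Stopping survival contact stops much of what feeds that page.
- SAE reporting is a partial backstop. Table 8-6 note 10 says "The SAE reporting period is up to 5 months after the last nivolumab administration" and Protocol 9.2.2 says "Any SAE occurring up to 5 months from the last nivolumab infusion date will be reported". Under 9.3 an SAE already reported is followed "Until the event is otherwise explained regardless of whether the patient is still participating in the study".
- However, Protocol 8.2.2.1 makes AE recording over that period conditional on end-of-life care not having begun, and 9.1.1 says lack of efficacy is not an AE. A death from progression in this subgroup may therefore never be entered as an SAE.

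**3. Direction**

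Let a share h of deaths be censored a time d before death and never recovered, with h and d unrelated to survival time. With true density f and survival S, the hazard that Kaplan-Meier sees at time t is

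(1−h)·f(t) / [(1−h)·S(t) + h·S(t+d)].

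This is below f(t)/S(t) whenever h > 0 and S(t+d) > 0. In large samples the OS curve is too high whatever the values of h and d.

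**4. Illustration of size (every input is an assumption)**

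For exponential survival with L = ln 2/median, apparent median = true median × [(1−h) + h·exp(−L·d)]/(1−h).

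- True median 8 months, d = 1 month: L = 0.0866 and exp(−L) = 0.917.
- h = 5%: 8 × (0.95 + 0.0459)/0.95 = 8.39.
- h = 10%: 8 × (0.90 + 0.0917)/0.90 = 8.82.

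A simulation of 400,000 patients used true medians of 6, 9 and 12 months; 20, 40 or 60% entering end-of-life care; a mean of one month from then to death; and none or half of those deaths recovered. Results for a true median of 9 months (true 12-month OS 39.7%):

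| Entering end-of-life care | Median, half recovered | Median, none recovered |
|---|---|---|
| 20% | 9.9 | 11.1 |
| 40% | 11.1 | 14.6 |
| 60% | 12.5 | 21.5 |

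Twelve-month OS ranged from 43.2% to 67.9% over these six cases. All 18 scenarios (3 medians × 3 shares × 2 recovery rates) overstated OS. The algebra agrees: with an exponential lead time of mean 1 month, exp(−L·d) is replaced by 1/(1+L) = 1/1.0770 = 0.9285, and 9 × (0.8 + 0.2 × 0.9285)/0.8 = 11.1.

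**5. Sampling error for comparison**

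If every patient is an event, the approximate 95% interval of an 8-month median is 8·exp(±1.96/√n): 4.0 to 16.0 at n = 8 and 4.8 to 13.3 at n = 15.

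**The case against.** The strongest reply is that 8.3.2.2 is the operative follow-up section, names end-of-life care, and limits the consequence to on-site visits. Several specific passages stand against one item in a general list. Many patients entering end-of-life care will already have progressed or started new therapy, and for them contact is mandatory with no stop at end-of-life care. Section 8.3.2.2 also lets the site approach the primary physician or family. It announces a scheme relating EOT to EOS, a figure missing from the available text that may settle the matter. OS is secondary, cohorts are small, and nothing shows that a site closed patients this way.

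Most of this stands, and it keeps the point minor. It does not remove the contradiction: the 8.4 wording is mandatory, and the same patient cannot both leave the study and stay under survival contact.

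Three stronger readings are tempting and are not supported:

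- A reader might infer that no patient entering end-of-life care need be contacted, because the triggers omit that event. The omission matters only for patients without progression or new therapy.
- A reader might infer that every death beyond the SAE period goes undocumented. The eCRF Death page is a separate route, so only its supply of information is at risk.
- A reader might use the 5-month SAE period to calculate how many deaths are recovered. Sections 8.2.2.1 and 9.1.1 leave it unclear whether these deaths would be reported as SAEs at all, so such a calculation has no footing in the documents.

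**Conclusion.** The conflict between 8.4 item 3 and 8.3.2.2 is in the current text. Applied literally, item 3 would produce informative censoring and an upward bias in OS. That conclusion rests on two conditions: a site follows item 3, and some of the resulting deaths are not documented another way. The documents establish neither, so it would be wrong to infer that this trial's OS results are in fact biased.

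The size cannot be derived. The illustrations run from a few tenths of a month to more than a doubling of the median, depending wholly on assumed shares and recovery. With 5 to 10% of deaths lost, the shift is well inside the sampling error of a cohort of 8 to 15 patients. Confirmed ORR, the futility rules and the efficacy boundary do not depend on this. Severity is minor, and the correction is cheap.

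**What to change.** 1. Reconcile 8.4 item 3 with 8.3.2.2: the start of end-of-life care ends on-site visits and assessments, but survival-status collection continues to the end of the Main study period unless consent is withdrawn.
2. Add the start of end-of-life care as a survival-contact trigger in the 8.3.2.2 bullet, the synopsis and the follow-up notes to Tables 1-1 and 8-6, so that patients without earlier progression or new therapy are covered by a requirement.
3. Before the final OS analysis, identify patients closed for this reason from the discontinuation reasons that SAP 10.1 already tabulates, and seek vital status where consent allows. SAP 4.3 already describes the Part B cohorts as futile, so this retrospective step matters most. If there are no such patients, a sentence saying so closes the point.
4. Optional: an OS sensitivity analysis in SAP 17.2.4 that counts an event at closure only for patients closed for end-of-life care without a documented death. It dates the event before death, so it is a lower bound. With a true median of 8 months and no recovery it gave 7.95 (5% closed, one month before death) down to 6.57 (50% closed, three months before).

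The cost is protocol wording, a few more contacts of a kind already planned, and one vital-status check. No treatment rule changes.
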